7.2.4. Study Day 8 ± 1 Day

On Study Day 8, the subject should bring their used dropper bottles with any unused medications with them for purposes of drug accountability. At the end of the Study Day 8 Visit the study medication box will be re-dispensed with the unopened medication.

The subjects will be asked if they had any problems with their eyes from the last visit, and if there have been any changes in their medical condition, or concomitant medications since their last visit. ***Any changes in the condition of the subject are recorded as an adverse event.***

In addition, on Study Day 8:

- Review of concomitant medications at 8AM.
- IOP measurements will be done at 8AM, 10AM and 4PM. All IOP measurements have a window of ± 15 minutes with at least 2 hours between the 8AM and 10AM assessments. IOP will be measured twice in both eyes at each timepoint. The mean value at each timepoint for the study eye will be used in efficacy assessments. If the difference in the two IOP measurements is > 5 mmHg, a third measurement will be obtained, and the three values averaged.
- Pupil diameter, near and distance visual acuity, resting heart rate and blood pressure are measured at 8AM. Blood pressure, using the same arm, same cuff size appropriate for arm circumference throughout the study, and heart rate should be measured after at least 3 minutes rest in the sitting position. If HR or BP are outside the normal range (see Exclusion Criteria – Systemic #7 and #8), they may be repeated only once following at least a 5 minute rest period in the sitting position.
- Eye redness (conjunctival hyperemia) visually checked at each timepoint using [REDACTED] scale.
- Adverse Events will be reviewed at each timepoint.

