7.2.3. Qualification Visit/Baseline (Day 1)

At the Qualification/Baseline Visit, the subject will be asked how do his/her eyes feel, and if there have been any changes in their medical condition, or concomitant medications since their last visit. Any adverse changes in the condition of the subject at this visit are recorded in the Medical/Ophthalmic History CRF.

At the Qualification/Baseline Visit:

- Females of childbearing potential will take a urine pregnancy test at 8AM.
- Review of concomitant medications at 8AM.
- IOP measurements using a [REDACTED] at the Baseline visit and both Treatment-study visits will be done at 8AM, 10AM and 4PM. All IOP measurements have a window of ± 15 minutes with at least 2 hours between the 8AM and 10AM assessments. IOP will be measured twice in both eyes at each timepoint. The mean value at each timepoint for the study eye will be used in efficacy assessments. If the difference in the two IOP measurements is >5 mmHg, a third measurement will be obtained, and the three values averaged.
- Pupil diameter, using a [REDACTED], near visual acuity using a standard chart held at 14 inches and distance visual acuity with ETDRS are measured at 8AM.
- Resting HR and BP are measured at 8AM and 4PM. Blood pressure, using the same arm, same cuff size appropriate for arm circumference throughout the study, and heart rate should be measured after at least 3 minutes rest in the sitting position. If HR or BP are outside the normal range (see Exclusion Criteria – Systemic #7 and #8), they may be repeated only once following at least a 5 minute rest period in the sitting position.
- Eye redness (conjunctival hyperemia) visually checked at 8AM, 10AM and 4PM using [REDACTED]
- Adverse events will be reviewed at each timepoint.

To continue in the study, the subject must have a mean IOP ≥ 22 mmHg at 8AM and ≥ 19 mmHg at 10AM and 4PM in the study eye **after the washout period** (if required) at the Qualification Visit (8AM).

Subjects may qualify in either eye. The eye with the higher IOP at the Qualification Visit at 8AM is designated as the study eye for the efficacy endpoints. In the case where both eyes have the same IOP, the study eye will be the RIGHT eye. See Section 9 for more information on statistical analysis. ALL TREATMENTS WILL BE ADMINISTERED TO BOTH EYES (O.U.).

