8.3.1. Adverse event definitions

The following definitions of terms apply to this section:

Adverse event means any untoward medical occurrence associated with the use of a drug in humans, whether or not considered drug related.

Life-threatening adverse event or life-threatening suspected adverse reaction. An adverse event or suspected adverse reaction is considered “life-threatening” if, in the view of either the investigator or sponsor, its occurrence places the subject or subject at immediate risk of death. It does not include an adverse event or suspected adverse reaction that, had it occurred in a more severe form, might have caused death.

Serious adverse event or serious suspected adverse reaction. An adverse event or suspected adverse reaction is considered “serious” if, in the view of either the investigator or sponsor, it results in any of the following outcomes:

- Death.
- A life-threatening adverse event.
- Inpatient hospitalization or prolongation of existing hospitalization.
- A persistent or significant incapacity or substantial disruption of the ability to conduct normal life functions.
- A congenital anomaly/birth defect.

Important medical events that may not result in death, be life-threatening, or require hospitalization may be considered serious when, based upon appropriate medical judgment, they may jeopardize the subject or subject may require medical or surgical intervention to prevent one of the outcomes listed in this definition.

Suspected adverse reaction means any adverse event for which there is a reasonable possibility that the drug caused the adverse event. For the purposes of IND safety reporting, “reasonable possibility” means there is evidence to suggest a causal relationship between the drug and the adverse event. Suspected adverse reaction implies a lesser degree of certainty about causality than adverse reaction, which means any adverse event caused by a drug.

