Unexpected adverse event or unexpected suspected adverse reaction. An adverse event or suspected adverse reaction is considered “unexpected” if it is not listed in the investigator brochure or is not listed at the specificity or severity that has been observed; or, if an investigator brochure is not required or available, is not consistent with the risk information described in the general investigational plan or elsewhere in the current application, as amended. “Unexpected,” as used in this definition, also refers to adverse events or suspected adverse reactions that are mentioned in the investigator brochure as occurring with a class of drugs or as anticipated from the pharmacological properties of the drug but are not specifically mentioned as occurring with the particular drug under investigation.

Any medical condition present prior to administration of the masked study medication which remains unchanged or improved should NOT be recorded as an adverse event at subsequent visits.

As noted in Section 7.2.1, any change in their Baseline health status that is not considered to be an adverse event should be recorded on the Medical History page of the CRF (e.g., the subject has been diagnosed with cancer).

The study medication relationship for each adverse event/adverse reaction should be determined by the Investigator using these explanations:

- **Not Related:** The event is clearly related to other factors such as subject's clinical condition, therapeutic interventions, concomitant disease or therapy administered to the subject and does not follow a known response pattern to the product.
- **Possibly Related:** The event follows a reasonable, temporal sequence from the time of study medication administration and/or follows a known response pattern to the study medication but could have been produced by other factors such as the subject's clinical state, therapeutic interventions or concomitant therapy administered to the subject.

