### **10.1. Adverse Events**

Adverse events will be coded using MedDRA, Version 22.0.

Treatment-emergent adverse events (TEAEs) are defined as any adverse event that begins or worsens after initiation of the investigational product and through the subject's last study visit (study completion or early termination) or follow-up telephone call. Serious adverse events will be recorded from the date of informed consent, throughout the clinical trial.

If the onset of an AE is on or after the date of first dose of study medication, or increasing in severity after first dose of study medication, then the AE will be considered treatment-emergent.

Only TEAEs will be summarized; all AEs (TEAE, non-TEAE) will be included in a by-subject listing.

The number and percent of subjects with any TEAEs will be summarized by system organ class and preferred term by treatment group and overall. At each level of tabulation (ex. at the preferred term level) subjects will be counted only once if they had more than one such event reported during the AE collection period.

Note that in MedDRA, ocular events are coded to the SOC of “special senses”. Thus, using SOC in the summaries will provide a separation of ocular and non-ocular adverse events.

The following summary tables will be presented for TEAE data:

- Overall summary of TEAEs
- Summary table of TEAEs by SOC and PT
- Summary table of TEAEs by highest relationship level to study drug by SOC and PT (not related, possibly related, related)
- Summary table of TEAEs by maximum severity by SOC and PT (mild, moderate, severe)
- Summary table of serious TEAEs by SOC and PT
- Summary table of TEAEs leading to withdrawal from the study by SOC and PT
- Summary table of TEAEs leading to study medication discontinuation by SOC and PT

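### The post-dose visit sections tell sites to record every change in condition as an adverse event, contrary to Protocol 8.3.1, so non-adverse changes may be recorded inconsistently

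*Protocol*

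**What the plan says.** **Visit sections.** Protocol 7.2.4 (Day 8), 7.2.5 (Day 15), 7.2.6 (Day 16) and 7.2.7 (Day 22 call) carry the same emphasised sentence: "Any changes in the condition of the subject are recorded as an adverse event". In each it follows a question about eye problems and about any change in medical condition or concomitant medication.

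**Baseline section.** Protocol 7.2.3 is narrower and sends the information elsewhere: "Any adverse changes in the condition of the subject at this visit are recorded in the Medical/Ophthalmic History CRF".

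**Definitions.** Protocol 8.3.1 opens with "Adverse event means any untoward medical occurrence associated with the use of a drug in humans". It then says that a condition present before masked medication which "remains unchanged or improved should NOT be recorded as an adverse event at subsequent visits". It also provides a separate destination: "any change in their Baseline health status that is not considered to be an adverse event should be recorded on the Medical History page".

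**Analysis.** SAP 10.1 defines a treatment-emergent adverse event (TEAE) as one that begins or worsens after the investigational product is started. The working rule is "If the onset of an AE is on or after the date of first dose of study medication", or an increase in severity after that dose. It adds: "Only TEAEs will be summarized; all AEs (TEAE, non-TEAE) will be included in a by-subject listing".

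**The concern.** Adverse events are one of the primary safety measures (Protocol 4.1; SAP 4.2.1). No statistical analysis of safety is planned (Protocol 9.3.5, Analysis of Safety) and there is no safety monitoring committee (SAP 7.4.2). The counts and percentages in the TEAE tables are therefore the main adverse-event readout, and they depend on sites sharing one rule for what goes on the form.

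The visit sections are the text that staff have in hand when they question the subject. Read literally, they call for an adverse event record for any change, including one for the better. Section 8.3.1 forbids that. A site working from the visit pages and a site working from 8.3.1 would treat the same subject differently, and with approximately 5 sites and 40 subjects a single site's habit could show in the tables.

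**Working it through.** **1. Where the two texts agree and where they conflict**

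| What the subject reports after dosing | Visit sections 7.2.4 to 7.2.7 | Section 8.3.1 |
|---|---|---|
| New untoward event | Record as adverse event | Record as adverse event |
| Existing condition worse | Record as adverse event | Record as adverse event |
| Existing condition unchanged | No change, nothing to record | Not an adverse event |
| Existing condition better | Record as adverse event | Must not be recorded as one |
| Other change in health status judged not to be an adverse event | Record as adverse event | Medical History page |

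The conflict is confined to the last two rows. No section gives precedence. Section 8.3.1 attributes its Medical History route to Section 7.2.1, but that section contains no such text, so the cross-reference does not settle the matter.

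**2. What happens to such a record under SAP 10.1**

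- The site follows 8.3.1: there is no adverse event record.
- The site logs the improved condition under its true, pre-dose start date with no rise in severity: it neither began nor worsened after dosing, so it is not a TEAE and appears only in the by-subject listing.
- The site logs the change as a new event with a post-dose start date: it meets the onset rule and is tabulated. The SAP has no step that asks whether the record was untoward.

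Only the third route reaches the TEAE tables.

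**3. What one record is worth**

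Inputs from Protocol 9.1: 36 completers, 10% drop-out, 1:1 allocation. The plan's own total is reproduced: 36 / (1 − 0.10) = 40 randomized, or 40 / 2 = 20 per arm. If all are dosed, the Safety Population has about 20 per arm and one subject is 1 / 20 = 5 percentage points.

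That is the effect on the any-TEAE rate only for a subject with no other TEAE. SAP 10.1 counts a subject once at each level of tabulation, so a subject who already has a TEAE does not move the any-TEAE rate, although the preferred-term row for the record still gains a subject.

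**4. Why no arm difference can be stated**

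The documents give neither a background TEAE rate nor a rate of recorded improvements. As an assumption, let *b* be the proportion with a genuine TEAE and *i* the proportion with an improvement logged as a new event, independent of each other. Then

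P(any TEAE) = 1 − (1 − *b*)(1 − *i*), and the rise caused by the misrecording is *i*(1 − *b*).

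With *i* = 5% (one subject in 20):

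| *b* | P(any TEAE) | Rise |
|---|---|---|
| 10% | 14.5% | 4.5 points |
| 30% | 33.5% | 3.5 points |
| 50% | 52.5% | 2.5 points |

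If *b* and *i* are the same in both arms, both rates rise and the difference is 0. If *i* is assumed to be 5% in one arm and 15% in the other, the false difference is 9, 7 and 5 points at *b* = 10%, 30% and 50%. Its sign depends only on which arm is given the 15%. These figures show sensitivity and are not estimates.

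**The case against.** **The case that this is harmless.** Adverse event is a defined term, and 8.3.1 contains a specific prohibition that most readers would apply over one general sentence in the visit sections. The form hardly accommodates a benefit: severity is graded by discomfort, and the outcome codes describe recovery, persistence, death or unknown. Protocol 13.2 provides validation checks and queries. The eye question asks about problems, so it does not invite reports of benefit. Vision, pupil diameter and IOP are recorded as efficacy measurements in their own right.

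**What stands.** These points make a literal reading less likely and limit its effect. They do not remove the conflict. The second question, about change in medical condition, is not limited to problems. The checks in 13.2 are aimed at missing or inconsistent data, and a fully completed form for an improvement need not trigger one. One qualification to the Medical History route is fair: it speaks of baseline health status, so it may be meant for pre-dose changes only. The bar on improved conditions expressly covers subsequent visits and does not depend on that reading.

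**Stronger readings that the documents do not support.** A reader might infer that every improved complaint becomes a TEAE. It does not: under SAP 10.1 an event must begin or worsen after dosing, so an improved pre-existing complaint reaches the tables only if it is logged as a new post-dose event. A reader might also infer that Nyxol's harm would be overstated, because Protocol 2.2 anticipates improvement in signs and symptoms and visual performance is an objective. The documents give no rate of reported improvement in either arm, the instruction is identical in both arms and treatment is masked. Equal rates create no difference.

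**Conclusion.** The contradiction is real and can be read directly from the text: four visit sections against 8.3.1, for improved conditions and for other changes that are not adverse events. Its supportable consequence is inconsistent recording between sites, with possible contamination of the TEAE tables by records that are not untoward. That contamination requires two things: a site that follows the visit text literally, and a record entered as a new event with a post-dose start date.

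The size cannot be derived from the documents. The only firm figure is that one subject with no other TEAE is worth 5 percentage points of an arm's any-TEAE rate, assuming about 20 dosed subjects per arm. No direction by arm is supported. The primary endpoint, the sample size and every planned test are unaffected. It is a modest fault in the recording rule for a primary safety measure, and worth correcting because the correction is so small.

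**What to change.** In Protocol 7.2.4, 7.2.5, 7.2.6 and 7.2.7, replace the sentence with: *Any untoward change or worsening in the subject's condition (see 8.3.1) is recorded as an adverse event.* Keep the Medical History route for changes that are not adverse events, and correct the reference in 8.3.1 to Section 7.2.1, which does not contain that text.

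The cost is a minor protocol amendment under Protocol 13.5, with approval and notice to the IRB. No assessment or analysis changes. If data have already been collected, a masked review of adverse event verbatim terms before unmasking would serve the same purpose. It could run alongside the blinded deviation review that SAP 8.2 already plans before database lock.

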7.2.5. Study Day 15 \pm 1 Day

On Study Day 15, the subject should bring their used dropper bottles and any unused medications with them for purposes of drug accountability.

The subjects will be asked if they had any problems with their eyes from the last visit, and if there have been any changes in their medical condition, or concomitant medications since their last visit. ***Any changes in the condition of the subject are recorded as an adverse event.***

In addition, on Study Day 15:

- Review of concomitant medications and a urine pregnancy test at 8AM.
- IOP measurements will be done at 8AM, 10AM and 4PM. All IOP measurements have a window of ± 15 minutes with at least 2 hours between the 8AM and 10AM assessments. IOP will be measured twice in both eyes at each timepoint. The mean value at each timepoint for the study eye will be used in efficacy assessments. If the difference in the two IOP measurements is >5 mmHg, a third measurement will be obtained, and the three values averaged.
- Pupil diameter, near and distance visual acuity, resting heart rate and blood pressure are measured at 8AM. Blood pressure, using the same arm, same cuff size appropriate for arm circumference throughout the study, and heart rate should be measured after at least 3 minutes rest in the sitting position. If HR or BP are outside the normal range (see

Exclusion Criteria – Systemic #7 and #8), they may be repeated only once following at least a 5 minute rest period in the sitting position.

- Eye redness (conjunctival hyperemia) visually checked at each timepoint [REDACTED]
- Adverse Events will be reviewed at each timepoint.
- Distance and near visual acuity, pupil diameter, and a complete ophthalmic examination, including biomicroscopy will also be performed at 4 PM.

Subjects completing their Day 15 Visit should be instructed **not** to resume their original glaucoma medication(s) until after completion of the Day 22 Follow-up phone call.

7.2.6. Follow-up Visit (Day 16)

The subjects will be asked if they had any problems with their eyes from the last visit, and if there have been any changes in their medical condition, or concomitant medications since their last visit. *Any changes in the condition of the subject are recorded as an adverse event.*

In addition, on Study Day 16:

- Review of concomitant medications at 8AM.
- IOP is measured twice in the study eye at 8AM \pm 15 minutes and the two values are averaged. If the difference in the two IOP measurements is >5 mm Hg, a third measurement is obtained, and the three values are averaged.
- Pupil diameter, near and distance visual acuity, resting heart rate and blood pressure are measured at 8AM. Blood pressure, using the same arm, same cuff size appropriate for arm circumference throughout the study, and heart rate should be measured after at least 3 minutes rest in the sitting position. If HR or BP are outside the normal range (see Exclusion Criteria – Systemic #7 and #8), they may be repeated only once following at least a 5 minute rest period in the sitting position.
- Eye redness (conjunctival hyperemia) visually checked at each timepoint using [REDACTED]
- Adverse Events will be reviewed at 8AM.

Subjects completing their Day 16 Visit should be reminded **not** to resume their original glaucoma medication(s) until after completion of the Day 22 Follow-up phone call.

7.2.7. Follow-up phone call (Day 22)

One week after their last dose, subjects will be called and asked if they had any problems with their eyes from the last visit including whether their eyes are red, and if there have been any changes in their medical condition, or concomitant medications since their last visit. *Any changes in the condition of the subject are recorded as an adverse event.*

If an adverse event/reaction is unresolved at the time of the last visit or if a subject reports a worsening of symptoms, every effort should be made to follow up until the adverse event/adverse reaction is resolved or stabilized, the subject is lost to follow-up, or there is other resolution to the event.

All subjects should be advised to resume their glaucoma medications during this follow-up phone call.

7.2.8. Unscheduled Visits

An Unscheduled Visit may be any visit to the Investigator other than the specific visits requested in the protocol as possibly required for the subject's ophthalmic condition. The Investigator will perform all procedures necessary to evaluate the study participant at these visits and record any adverse events in the CRF.

As noted in Section 4.9, every possible effort should be made by investigators to assure that subjects who discontinue early from the study have a final visit that includes all examinations listed for the Follow-up Visit.

7.2.9. Visit variation

Visits on Day 8 and 15 may be 1 day early or late. If the visit is late, the subject should be advised to take an additional dose from one of the 2 spare dropper bottles provided in the study medication box the night before the visit. The subject should then empty the remaining contents and store the opened bottle in the baggie provided and place it in the medication box for return to the study site at their next visit. If the Day 15 Visit occurs one day early or late, the Day 16 Visit and the Day 22 telephone call should be adjusted accordingly.

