4.2. Description and schedule of visits and procedures

Approximately 40 subjects with either OAG or OHT will be randomized, for a target of 36 completed subjects. Subjects will be randomized in a 1:1 ratio to receive 1 % Nyxol or placebo once daily for 14 days beginning at 8PM to 10PM on Day 1 and continuing through Day 14. Efficacy evaluations (IOP) will take place at the Baseline and the Treatment-study Visit days (Day 8 ± 1 Day and Day 15 ± 1 Day) at 8AM, 10AM, and 4PM. All IOP measurements have a window of ± 15 minutes with at least 2 hours between the 8AM and 10AM assessments. There will be Follow-up Visits on Day 16 at 8AM ± 15 minutes and by phone on Day 22 (7 days after the last Treatment-study Visit).

Study procedures are shown in detail in Table 1:

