4.4.3. Study medication accountability

4.4.3.1. Receipt and disposition of study medication

The Investigator or designee (e.g., study coordinator or pharmacist) will maintain a full accountability record for the study medication and will be responsible for recording the receipt, dispensing, and return of all supplies of the study drug using the inventories supplied by the Sponsor. Each subject will receive sufficient study medication for the duration of the trial. A Study Medication Box will be dispensed at Baseline Visit (Day 1). As described in Section 7.2.3, the subject will empty any remaining contents from the unit-dose dropper bottle following each instillation and will return in baggies in the original boxes ALL opened bottles as well as any unopened study medication at Treatment-study Visits (Day 8 ± 1 Day and Day 15 ± 1 Day). At the Day 8 Visit, the box will be re-dispensed to the subject following study drug accountability and removal of opened study medication materials. Study medication accountability will again be conducted at the Day 15 Visit, but the box will not be re-dispensed. The Investigator or designee will account for all received and returned study medication. The monitor will review dispensing and study medication accountability records during site visits and at the completion of the study and note any discrepancies. All investigational study medication must be stored in a secure facility, with access limited to the Investigator and authorized staff.

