6.1. Treatment adherence

All subjects will be instructed on the importance of following the once-a-day dosing regimen. Beginning the day of the Baseline Visit (Day 1) subjects will instill one drop of study medication in each eye at 8PM to 10PM and repeat this procedure 13 times for a total of 14 doses. Subjects are to bring unused bottles into the study site on the Day 8 Visit and the Day 15 Visit. Treatment adherence will be measured by counting the dropper bottles at the start of the study, and those remaining at each study visit.

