#### **8.6. Treatment Compliance and Exposure**

Continuous descriptive summaries for total exposure to study drug (in days) and percentage compliance will be presented for the Safety Population by treatment group. Exposure to study drug will be determined by counting the total number of used bottles returned.

Compliance will be determined by calculating the percent of used bottles returned to the total that should have been used during the treatment period.

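### The late-visit rule in Protocol 7.2.9 does not separate Day 8 from Day 15: read literally, a late Day 8 visit brings two doses on one evening, and under any reading the stated total of 14 doses depends on when the Day 15 visit falls

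*Protocol*

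**What the plan says.** Protocol 4.2 schedules dosing "once daily for 14 days beginning at 8PM to 10PM on Day 1 and continuing through Day 14". Section 6 repeats this, SAP 5.1 does the same, and Protocol 6.1 has the subject dose on Day 1 and "repeat this procedure 13 times for a total of 14 doses". Section 7.2.3 adds one new unit-dose bottle per evening, with doses about a day apart.

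Section 7.2.9 then covers shifted visits. It opens with both visits, "Visits on Day 8 and 15 may be 1 day early or late", and continues: "If the visit is late, the subject should be advised to take an additional dose from one of the 2 spare dropper bottles provided", with that dose placed on the preceding night. It does not say which of the two visits is meant. Its last sentence does single out Day 15, but only to move the Day 16 visit and the Day 22 call.

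On supply, Section 4.4.3.1 says "Each subject will receive sufficient study medication for the duration of the trial", dispensed at Baseline. For the end of treatment it says "Study medication accountability will again be conducted at the Day 15 Visit, but the box will not be re-dispensed".

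SAP 8.6 defines compliance as "the percent of used bottles returned to the total that should have been used during the treatment period" and takes exposure in days from the number of used bottles. It does not say what the expected number is when a visit moves. Protocol 4.8 defines a completed subject partly by completion of the planned dosing, again without reference to shifted visits.

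**The concern.** The late-visit sentence makes sense for Day 15, where a one-day delay leaves an evening with no scheduled dose before the measurements. It does not carry over to Day 8, which falls in mid-course: the evening before a late visit is an ordinary dosing evening and the subject already holds the bottle for it. An additional dose on that evening is a second dose.

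This instruction is passed to people dosing at home, so two sites could advise subjects differently and each point to the protocol. Where it is followed literally, the Day 8 measurements (IOP, redness, pupil diameter, acuity, heart rate and blood pressure) follow a doubled evening and are summarised together with data from once-daily subjects. A smaller matter is that the protocol states one dose total, while its own visit windows produce several.

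**Working it through.** **Inputs.** One dose per evening, Days 1 to 14 (Protocol 4.2, 6, 6.1). Day 8 visit permitted on Day 7, 8 or 9; Day 15 visit on Day 14, 15 or 16 (7.2.9). An added dose the night before a late visit (7.2.9). No dose on or after the evening of the Day 15 visit, because the box stays at the site (4.4.3.1).

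**The plan's own figure.** Evenings 1 to 14 give 14 doses, and 1 + 13 = 14. The stated total is reproduced for on-time visits.

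**Where the added dose falls.**
- Day 15 visit on Day 16: the night before is Day 15, outside Days 1–14. Scheduled 0, added 1, so 1 dose that evening.
- Day 8 visit on Day 9: the night before is Day 8, inside Days 1–14. Scheduled 1, added 1, so 2 doses that evening if read literally. Doses before the visit are then 8 + 1 = 9, against 8 if the spare merely supplies the scheduled dose.

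**Total doses for a fully adherent subject.** Total = evenings from Day 1 to the evening before the actual Day 15 visit, plus 1 under the literal reading if the Day 8 visit is late.

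| Day 8 visit | Day 15 visit | Literal reading | One dose per evening |
|---|---|---|---|
| Early or on time | Early (Day 14) | 13 | 13 |
| Early or on time | On time (Day 15) | 14 | 14 |
| Early or on time | Late (Day 16) | 15 | 15 |
| Late | Early | 13 + 1 = 14 | 13 |
| Late | On time | 14 + 1 = 15 | 14 |
| Late | Late | 15 + 1 = 16 | 15 |

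Only the late Day 8 rows differ between the readings, and only there does an evening hold two doses. The 13, 14 and 15 in the first three rows do not depend on the reading. The 14 in the fourth row arises by cancellation.

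**Timing.** From a dose at 8PM–10PM, the nominal Day 8 measurement times are 10–12 hours later (8AM), 12–14 hours (10AM) and 18–20 hours (4PM). IOP and redness are taken at all three; pupil diameter, acuity, heart rate and blood pressure at 8AM.

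**Analysis set.** The Full Analysis Set needs at least 11 doses with no two consecutive doses missed (SAP 7.1.1). The smallest total above is 13, so a fully adherent subject stays in under every combination.

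**The case against.** The best defence is that 7.2.9 should be read with the rest of the protocol. Sections 6.1 and 7.2.3 set once-a-day dosing from a single bottle per evening, so the late-visit sentence may only ensure that a dose precedes the visit, with the spares covering a longer interval. On that view a late Day 8 visit gives one dose that evening and 14 in all. This reading is available and a careful site might adopt it. But it requires the added dose not to be additional, and no text says that the spare replaces the scheduled dose or that the rule is confined to Day 15. It can equally be said that 14 is a nominal total and 7.2.9 the specific exception; that is fair, but the exception never states the totals it produces.

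Several stronger inferences are tempting and are not supported:
- *The primary analysis is compromised.* The rule creates no double evening before the Day 15 visit. The Day 8 efficacy endpoints are secondary, with p-values described as descriptive (Protocol 9.3.1), and safety data are not tested.
- *SAP compliance will be wrong.* Against a denominator of 14, totals of 13, 15 and 16 would read 13/14 = 92.9%, 15/14 = 107.1% and 16/14 = 114.3%. SAP 8.6 does not state 14, and its wording could be read per subject. The gap is that it does not say.
- *An adherent subject with an early visit is not a completer.* Planned dosing can reasonably include a permitted early visit, and the definition sets no analysis population.
- *Two spares show that doubling was intended.* Two spares fit either reading, or a simple margin.
- *A given number of subjects will be affected.* The documents give no late-visit rate. Any such count would also cover both arms, with about half on vehicle under 1:1 randomization.
- *A double dose would go unseen.* Opened bottles are counted at the Day 8 visit, so nine used after eight evenings would show, although a count cannot tell which evening took two.

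The schedule table and the case report forms are not in the available text; a clarifying note there cannot be excluded.

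**Conclusion.** The point holds as an internal conflict in a home-dosing instruction, of limited reach. As written, 7.2.9 covers a late Day 8 visit and, read literally, gives two doses on the Day 8 evening, against the schedule in Sections 4.2, 6, 6.1 and 7.2.3. This rests on two conditions: the Day 8 visit is late, and the word additional is taken at face value. When both hold, Day 8 secondary efficacy and safety data are affected; the primary endpoint and Full Analysis Set membership are not directly affected.

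The second part does not depend on the reading. With an on-time Day 8 visit, the protocol's own windows give 13, 14 or 15 doses, so the fixed total matches only an on-time Day 15 visit. This is chiefly a matter of bookkeeping for compliance and completion.

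**What to change.** Reconcile Protocol 7.2.9 with 4.2, 6, 6.1 and 7.2.3. State separately for the Day 8 and Day 15 visits whether the late-visit sentence applies, and give the number of doses due by each permitted visit day (Days 7, 8 and 9; Days 14, 15 and 16). Which dosing rule applies is for the sponsor to decide.

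In SAP 8.6, define the expected number of bottles as the doses due up to the subject's actual Day 15 visit under the reconciled rule. Read planned dosing in Protocol 4.8 the same way.

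Two further steps are best left out. Exposure as distinct dosing evenings cannot be derived from the bottle counts that the documents describe. Classing every two-bottle evening as a deviation would presume the answer to the dosing question.

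The cost is a short protocol clarification and one SAP sentence, with no added visits or subjects.
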